5.3 Electrocardiograms (unadjudicated)

ECG analyses will be performed on two sets of ECGs: all ECGs prior adjudication and selected triplicates from each timepoint after adjudication.

All un-adjudicated ECG data (PR, QRS, QT, QTcB, QTcF and HR) including H/L flags and overall ECG evaluation will be listed. The QT interval will be corrected using Fridericia's formula ($QTcF = QT/RR^{1/3}$) and Bazett's formula ($QTcB = QT/RR^{1/2}$).

For ECG variables, the change from baseline will be derived using the arithmetic mean value of each time-point triplicate minus baseline value, where baseline is the arithmetic mean of the three pre-dose QTcF values of Day 1.

Absolute (observed) values and changes from baseline in the ECG variables will be summarized by treatment group and timepoint.

Reference ranges for ECGs are as follows:

ECG Parameter	Normal Range Pulse
Rate (supine)	40–100 bpm Respiratory
Rate (supine) (supine)	8-20 breaths per min Heart Rate 40-100 bpm
PR interval	120–200 ms
QRS duration	≤120 ms
QTcF	≤450 ms

Furthermore, categorical analysis of QTcF data will be presented as follows:

- Absolute QTcF interval prolongation
 - QTcF interval > 450 ms
 - QTcF interval > 480 ms
 - QTcF interval > 500 ms
- Change from baseline in QTcF interval
 - QTcF interval increases from baseline > 30 ms
 - QTcF interval increases from baseline > 60 ms

Mean value of QTcF parameters will be plotted by dose group and time point.

Likewise, categorical analyses of other quantitative ECG parameters will be given. More specifically, an increase in PR from predose baseline >25% to a PR >200 ms; an increase in QRS from predose baseline >25% to a QRS >120 ms; a decrease in HR from predose baseline >25% to a HR <50 bpm or an increase in HR from predose baseline >25% to a HR >100 bpm will be summarised.

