The pharmacy staff preparing the investigational products will not be blinded to study drug assignment. During the study, the individual randomisation codes will be kept in the site's clinical trials pharmacy, accessible to the pharmacy personnel only. Upon completion of the study, after the database lock and after the blind is revealed, the randomisation list will be filed in the Trial Master File.

Sponsor staff involved in clinical decision-making (such as those involved in SRC decisions) will be blinded to study drug assignment.

Study numbers will not be reallocated once assigned.

4. General notes for statistical analyses

In general, descriptive statistics for continuous variables will include number of non-missing values (n), arithmetic mean, standard deviation (SD), median, minimum, and maximum.

Descriptive statistics for PK parameters will include number of observations, arithmetic mean (n), standard deviation (SD), arithmetic coefficient of variation (%CV), geometric mean, geometric %CV, median, minimum and maximum.

Categorical variables will be summarized using frequency counts and percentages.

For all tables, except PK parameter tables, descriptive statistics for minimum and maximum will be presented with the same decimal digits as the original data, and with 1 more decimal place than the original data for mean and median; SD will be reported with 2 more decimal places than the original data.

PK parameters will be presented as follows in the listing: C_{max} and T_{max} will be presented as given in the raw data; AUC_{0-t} , $AUC_{0-\infty}$, λ_z , $t_{1/2}$, CL or CL/F, and Vd or V_d/F will be presented with 3 decimal places. Descriptive statistics for PK parameters will be presented with decimal places as appropriate for the particular parameter and treatment group. SAS v9.3 or higher or Phoenix WinNonLin v7 or higher may be used for the determination of Pharmacokinetic parameters.

The analyses will be presented by treatment group. All collected data will be presented in by-subject listings. Listings will be ordered by treatment group and subject number and will include all randomized subjects.

Baseline will be defined as the last non-missing value among assessments recorded prior to first administration of study drug. Changes from baseline values will be calculated as the post-baseline assessment value minus the baseline value. Only observed values from scheduled time points will be used to create summary tables.

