5.4.2 Baseline

The average over the three pre-dose QTcF values of Day 1 will be used as baseline.

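### The SAP defines an ECG baseline only for QTcF, so the baseline for PR, QRS, HR, QT, QTcB and (if used) QTcS or J-Tpeak is left to the analyst

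*SAP*

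**What the plan says.** SAP 5.3 names the variables: "All un-adjudicated ECG data (PR, QRS, QT, QTcB, QTcF and HR) including H/L flags and overall ECG evaluation will be listed". It then gives a single derivation: "For ECG variables, the change from baseline will be derived using the arithmetic mean value of each time-point triplicate minus baseline value". The baseline in that derivation is specified from one parameter only: "where baseline is the arithmetic mean of the three pre-dose QTcF values of Day 1". The results are reported for the whole set: "Absolute (observed) values and changes from baseline in the ECG variables will be summarized by treatment group and timepoint". The same section counts outliers relative to a pre-dose baseline. For PR the rule is "an increase in PR from predose baseline >25% to a PR >200 ms"; the QRS rule has the same form, "an increase in QRS from predose baseline >25% to a QRS >120 ms", with matching rules for a fall in HR to below 50 bpm and a rise to above 100 bpm.

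For the adjudicated ECGs, SAP 5.4.2 says: "The average over the three pre-dose QTcF values of Day 1 will be used as baseline". Other parts of that analysis reach beyond QTcF:

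- SAP 5.4.3 summarises change from baseline for the quantitative ECG parameters generally.
- SAP 5.4.1 allows a study-specific correction (QTcS) to become primary.
- SAP 5.4.9 models corrected J-Tpeak.

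The only other baseline definition is the general one in SAP section 4: "Baseline will be defined as the last non-missing value among assessments recorded prior to first administration of study drug". Protocol 10.3 and 10.4.2 use the same outlier criteria and the same change-from-baseline summaries, but define no ECG baseline.

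**The concern.** A change score needs a baseline in the same parameter. As written, PR, QRS, HR, QT and QTcB are each compared with a QTcF mean, and for HR the units do not match. Changes in PR, QRS and QT are among the ECG intervals named in the primary safety endpoint.

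An analyst will almost certainly not program the literal rule, but the plan does not say what to do instead. One substitute copies the QTcF approach (the mean of three timepoints). The other follows section 4 (a single last value, which protocol Table 2 places at −2 h on Day 1). The choice would then be made outside the plan and could change small outlier counts.

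QTcS is a separate and conditional matter. Subtracting a QTcF baseline from QTcS gives plausible milliseconds with no unit mismatch, so the error would be harder to notice.

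**Working it through.** The plan states no figure to reproduce. The inputs below that are marked as assumed are not in the documents.

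**1. The literal rule.** Assume a mean pre-dose QTcF of 405 ms.

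- PR of 160 ms (assumed), unchanged after dosing: 160 − 405 = −245 ms, where the true change is 0.
- A rise of more than 25% needs a value above 1.25 × 405 = 506. A PR going from 150 to 210 ms is really +40%, but would read (210 − 405)/405 = −48%.
- A fall of more than 25% needs a value below 0.75 × 405 = 304. An HR going from 52 to 48 bpm is really −8%, but would read (48 − 405)/405 = −88%.

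These results show that the sentence cannot be applied to anything but QTcF. They do not predict what will be reported.

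**2. The two workable substitutes.** Let m be a subject's own mean over −3, −2.5 and −2 h, and l the value at −2 h.

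- The threshold for a rise of more than 25% is 1.25 m under one rule and 1.25 l under the other.
- The thresholds differ by 1.25 × (l − m), so each 1 ms between l and m moves the PR or QRS threshold by 1.25 ms.
- For an assumed PR mean of 160 ms, 1.25 × 160 = 200 ms, which is also the absolute limit. If l is higher than m, the section 4 rule raises the bar above 200 ms, and a post-dose value between the two thresholds is counted under one rule and not under the other.

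SAP 3.1 gives 8 subjects on Treatment 1 and a target of 12 on each other treatment. One reclassified subject is 1/8 = 12.5 or 1/12 = 8.3 percentage points. The documents give no within-subject variability, so how often this would happen cannot be stated.

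**3. QTcS with a QTcF baseline.** With no true change, the offset is QTcS − QTcF = 405 × RR^(1/3 − β) − 405, where RR = 60/HR in seconds. The 405 ms, HR and β values are assumed.

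| Pre-dose HR | β = 0.30 | β = 0.40 | β = 0.45 |
|---|---|---|---|
| 55 | +1.2 ms | −2.3 ms | −4.1 ms |
| 60 | 0 | 0 | 0 |
| 70 | −2.1 ms | +4.2 ms | +7.3 ms |

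The offset is constant within a subject. It therefore drops out of the Day 3 contrasts in SAP 5.4.8, which are taken against the Day 3 pre-dose estimate, and largely cancels in comparisons with placebo. It does not drop out of the Day 1 time effects, which SAP 5.4.8 uses without such a difference. There it would act against an expected shortening of 5–10 ms: a positive offset hides shortening and a negative one exaggerates it.

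**4. What is untouched.** For QTcF the baseline is correct. QTcF changes, the >30 and >60 ms categories and the absolute QTcF categories do not change.

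**The case against.** The strongest reply is that the intent is clear. A percentage rise in PR from baseline only makes sense against baseline PR, and a bpm value minus a millisecond value would be spotted at once. Protocol 10.3 has the same criteria without the QTcF-only sentence. Protocol 10.4.1 says that the analyses are repeated with the replacement correction, and 10.4.3 uses the change in QTc together with baseline QTc, which suggests that the baseline follows the correction chosen. SAP 5.4.9 models J-Tpeak in the same way as QTc, which points the same way. Absolute values and high/low flags are reported regardless, and a Research Physician reviews every ECG.

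Most of this stands. A reader might infer that the trial will report no PR or QRS outliers at all and will flag every HR below 50 bpm. The documents do not support that inference: it needs an implementation that the outlier wording itself contradicts, and any flagged proportion would need an HR distribution that the documents do not give. Nor do they tie the >25% criteria to what counts as clinically significant in the primary endpoint, and HR is not among the ECG intervals named there.

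The reply does not settle which own-parameter baseline applies. Knowing that PR is compared with PR does not say whether that is the three-timepoint mean or the last value.

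**Conclusion.** This is a wording defect, of minor severity. SAP 5.3 and 5.4.2 define no usable baseline for any ECG parameter except QTcF, and the section 4 fallback is a different statistic from the three-timepoint mean used for QTcF. The practical effect is confined to subjects near the 25% threshold, where one subject moves an incidence by 8.3 to 12.5 percentage points.

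A reader might also infer that assay sensitivity is compromised. That holds only if three things happen together: HR changes by more than 10 bpm against placebo, QTcS has the smaller mean squared slope in SAP 5.4.1, and the QTcF baseline is then kept. Even so, the shift is near 0 if mean pre-dose HR is about 60. It reaches about −2 to +7 ms only if mean HR is about 70, for exponents of 0.30 to 0.45. The documents give neither the mean HR nor the exponent.

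**What to change.** In SAP 5.3 and 5.4.2, replace the baseline sentence with:

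> For each ECG parameter (HR, PR, QRS, QT, QTcB, QTcF, and QTcS or J-Tpeakc where used), baseline is the mean of that same parameter over the three Day 1 pre-dose timepoints (−3, −2.5 and −2 h), each being the mean of its triplicate. This replaces the general baseline of section 4 for ECG.

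This extends the SAP's own QTcF approach to the other parameters. It costs one sentence in two places, needs no new data and leaves the QTcF results unchanged.

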5.4 Analysis of Adjudicated ECG

Intensive cardiac assessments will be performed using food effects on the ECG to establish assay sensitivity. Analysis of drug related QT/QTc interval changes relative to plasma PK concentrations will be conducted. The principles of this analysis follow the statistical methods described by Garnett et al., 2018 [1]. The ECG utilised for this analysis require adjudication by qualified cardiologists in accordance with principles set out in the ICH E14 guideline and subsequent Q&A documents. All ECG recordings are in triplicate and will be compliant with the correct recording and manual adjudication of ECG in thorough QT/QTc studies. Below ECG analyses will be based on adjudicated selected triplicates from each time point.

Two complementary sets of analyses will be performed: a per timepoint analysis and a concentration-QTc analysis. While the first is based on minimal assumptions on the nature of the data, it has limited power to show the absence of a prolonging effect. On the other hand, the concentration-QTc analysis has shown to have this power, but it is based on more restrictive assumptions.

5.4.1 Heart rate correction

QTcF will be used for ECG analyses, unless there is a substantial heart rate effect, i.e. changes in HR compared to placebo of more than 10 bpm, in which case the correction used for QTc (the most appropriate heart rate correction) will be calculated. More specifically, a study specific correction (QTcS) will be calculated by fitting a linear mixed effects model of the form

$$\log(QT) \sim \log(RR) + 1$$

to the data from the individual time-points of the pre-dose data of all subjects. This model will have a random intercept and term for $\log(RR)$. The study specific effect will be determined from the fixed effect β of the $\log(RR)$ term and will result in a parabolic correction of the form

$$QTc = QT * RR^{-\beta}$$

To determine the primary correction method in this case, a linear mixed effects model of the form

$$QTc \sim RR + 1$$

with random intercept and RR per subject will be fitted to all non-baseline data using QTcF and QTcS. The mean of the squared individual slopes (MSS) (i.e. the individual regression coefficients) will be calculated and the correction method with the smaller MSS will be selected as primary.

Scatter plots of QT and QTc against RR will be produced to visualise the best correction formula.

Note: The study protocol mentioned that an individual correction of QTc would be applied but due to the small sample-size a study specific correction of QTc will be the method of choice if QTcF cannot be used.

5.4.2 Baseline

The average over the three pre-dose QTcF values of Day 1 will be used as baseline.

5.4.3 Descriptive Statistics

For the quantitative ECG parameters, descriptive statistics will be given by timepoint for absolute values and change from baseline by treatment group.

5.4.4 By timepoint analysis for QTc

A linear model of the form: $\Delta QTc \sim \text{treat} + \text{BL}$ will be fitted for each timepoint and the difference between each of the active treatments and placebo will be estimated based on this model with two-sided 90 % confidence intervals. In this model, treat is a factor with four levels: placebo, the two monotherapies and combination therapy, and BL is the centered baseline (i.e. the mean baseline across subjects is subtracted from each individual baseline).

5.4.5 Primary linear model

A series of linear mixed effects model will be fitted. The most comprehensive of these models will be of the form

$$\Delta QTcF \sim C_{ATV} + C_{AQ} + C_{PG} + C_{CG} + C_{DEAQ} + \text{treat} + T + BL$$

where $\Delta QTcF$ is the change from baseline of QTcF, C_{ATV} the plasma concentration of ATV, C_{AQ} the plasma concentration of AQ, C_{PG} the plasma concentration of PG, C_{CG} the plasma concentration of CG, C_{DEAQ} the plasma concentration of DEAQ, treat is a four-level factor with levels placebo, ATV-PG, AQ and ATV-PG + AQ (for placebo, the two monotherapies and the combination therapy respectively) and T is a discrete time effect with one level for each timepoint across study days – i.e. the same time at different days will have different values. This model will allow for treatment and time as categorical fixed effect factors. Concentrations of AQ, DEAQ and relevant analytes/metabolites will be used as covariates.

Note that including a treatment effect will allow some judgement on the appropriateness of the model, as a well-fitting linear model should have a non-significant treatment effect. BL is baseline value for each subject, with the mean across subjects subtracted. No fixed intercept will be allowed.

The model will have random effects per subject for the intercept and the concentration levels. An unstructured covariance matrix will be assumed. If this model does not converge, some or all of the random slopes will be removed, and further simplifications may be performed to reach convergence. Parameter estimation will be using the REML (Restricted Maximum Likelihood) method.

The Kenward-Roger approximation will be used to calculate degrees of freedom and any t-test-based quantities, in particular two-sided 90% confidence intervals for the model parameters.

From the above most comprehensive model, simplified models will be derived by omitting one or more concentration parameters. This will be performed in a stepwise way, by removing the concentration with the smallest absolute t-value from the model. As a result, a series of 5 models with 5 down to 1 concentration will be obtained. For each model, the AIC and the F-value of the treatment effect from an ANOVA will be obtained. If this F-value is significant at the 5 % level, the model will be excluded from the candidate set. For the models remaining, the model with smallest AIC will be chosen as primary.

Predictions of the effects on QTc of each monotherapy and for the combination therapy will be made at the geometric means of the individual C_{max} values and given together with two-sided 90 % confidence intervals. Predictions will be given for the primary model, and may also be given for other models of interest.

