2.1 Study objectives

The objectives of this study are:

Primary

- To assess the safety and tolerability of the approved curative dose of ATV-PG (once daily for 3 days) and the adult equivalent of the approved SMC dose of AQ (once daily for 3 days) when administered alone and in combination, in comparison with placebo.

Secondary

- To determine the pharmacokinetics (PK) of atovaquone (ATV), proguanil (PG) and cycloguanil (CG), and amodiaquine (AQ) and desethyl-amodiaquine (DEAQ) following administration of ATV-PG and AQ alone and in combination.
- To determine the relationship between AQ and DEAQ and ECG parameters and to evaluate any impact of the combination with ATV-PG on this relationship.

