2.2 Endpoints

Primary

- Safety and tolerability as measured by the incidence of treatment-emergent adverse events (TEAEs) including the clinical signs, nausea, vomiting and diarrhoea, proportion of subjects with clinically relevant changes in laboratory safety tests (haematology, chemistry (in particular ALT, AST and bilirubin increases) and urinalysis), proportion of subjects with morphological and/or rhythm abnormalities on electrocardiogram (ECG), proportion of subjects with clinically significant changes in ECG time intervals (PR, QRS, QT and QTc intervals) and proportion of subjects with clinically significant changes in vital signs (systolic blood pressure, diastolic blood pressure and pulse rate).

Secondary

- PK parameters derived by non-compartmental methods including maximum observed plasma concentration (C_{max}), time to maximum plasma concentration (t_{max}), area under the plasma concentration-time curve from time zero to last detectable plasma concentration (AUC_{0-t}), area under the plasma concentration-time curve from time zero extrapolated to infinity (AUC_{0-inf}), terminal elimination rate constant (λ_z), terminal elimination half-life ($t_{1/2}$).
- Baseline corrected QTc (ΔQTc) as a function of the concentrations of AQ and DEAQ when administered alone, and when administered in combination with ATV-PG.

3. Trial Design

The study is a randomized, double-blind, placebo controlled, parallel group study to determine the tolerability and safety of ATV-PG + AQ, ATV-PG + AQ placebo, ATV-PG placebo + AQ, and ATV-PG placebo + AQ placebo administered once daily for 3 days to healthy adult male and female subjects.

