5.4.6 Checking model assumptions

The key assumptions for the above model to be applicable are linearity of the concentration-QTc-relationship and the absence of hysteresis. These assumptions apply only if there is an effect of plasma concentrations on QTc. Therefore, if the predictions described above exclude an effect of more than 10 ms (i.e. the two-sided 90 % confidence interval for the prediction is completely below 10 ms) and

the per timepoint analysis described in 5.4.4 do not indicate a different result, the primary model will be accepted.

If, however, a prolongation beyond 10 ms cannot be excluded, the following will be performed:

Hysteresis: Simultaneous displays of the time courses of the placebo adjusted mean $\Delta QTcF$ ($\Delta\Delta QTcF$) and the (arithmetic) mean plasma concentrations will be prepared. Likewise, hysteresis loops, i.e. a plot of mean $\Delta\Delta QTc$ against the mean concentration for each timepoint will be presented. If there is a delay of the maximum of the mean $\Delta\Delta QTcF$ with respect to the mean concentration of all moieties included in the primary model, this is an indication for hysteresis. If there is a delay, it will be assumed that the model used is not appropriate.

Linearity: Linearity will be assessed from the decile plots (see below). In addition, if the treatment effect of all candidate models is significant on the 5 % level, a nonlinear e_{max} model will be fitted to the data. More specifically, this will be a model where each of the concentration terms in the linear model with lowest AIC is replaced by an e_{max} -term $aC(1+bC)$. In this model the only random effect per subject will be the intercept. Predictions will be based on this model or on the primary linear model, whichever fits better according to the Akaike Information Criterion and the t-value of the treatment effect. More specifically, if the e_{max} model has a non-significant treatment effect, while the linear one has a significant one, the e_{max} model will be used, otherwise, the one with the smaller AIC will be used.

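### No planned QTc model lets the AQ or DEAQ slope differ between AQ alone and the combination, and no combination-minus-AQ contrast with an interval is planned, so the objective on ATV-PG's impact gets no direct estimate

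*SAP*

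**What the plan says.** SAP 2.1 sets a secondary objective on the relation between AQ, DEAQ and ECG parameters, and "to evaluate any impact of the combination with ATV-PG on this relationship". SAP 2.2 defines the matching endpoint as baseline-corrected QTc "as a function of the concentrations of AQ and DEAQ when administered alone, and when administered in combination with ATV-PG".

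The analyses that serve this objective are:

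- **SAP 5.4.4.** A linear model at each timepoint with a four-level treatment factor and centred baseline, from which "the difference between each of the active treatments and placebo will be estimated based on this model with two-sided 90 % confidence intervals".
- **SAP 5.4.5, largest model.** After "The most comprehensive of these models will be of the form" comes ΔQTcF on the concentrations of ATV, AQ, PG, CG and DEAQ, plus treatment, time and baseline. Random slopes are per subject and may be removed for convergence.
- **SAP 5.4.5, other linear models.** "From the above most comprehensive model, simplified models will be derived by omitting one or more concentration parameters", each step "removing the concentration with the smallest absolute t-value from the model". A model with a significant treatment F-test leaves the candidate set.
- **SAP 5.4.5, predictions.** "Predictions of the effects on QTc of each monotherapy and for the combination therapy will be made at the geometric means of the individual" peak concentrations, each with a two-sided 90% interval.
- **SAP 5.4.6, fallback.** If every linear candidate fails the treatment test, "this will be a model where each of the concentration terms in the linear model with lowest AIC is replaced", one for one, with an e-max term.

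**The concern.** If the question is whether ATV-PG alters the AQ/DEAQ-QTc relation, the natural estimates are the difference in slope between the two AQ-containing arms and the difference in QTc effect between those arms. The plan reports neither with an interval. A reader would have to compare two separate predictions by eye, and both come from a model that forces a common slope.

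If the slopes truly differ, part of the difference is absorbed into the shared slope. The combination prediction is then too close to the AQ-alone prediction, and the AQ-alone prediction is shifted by the combination arm's data. That second effect matters because the notes to the EPS rule in Protocol 4.4 keep the AQ arm partly to obtain QTc data for other AQ combinations.

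**Working it through.** **1. Structure.** Set against the objective, each planned output gives the following.

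| Output | Slope change? | Combination minus AQ with interval? |
|---|---|---|
| 5.4.4 treatment differences | No concentration terms | No; each arm against placebo only |
| 5.4.5 largest model | No; one fixed slope per moiety | No |
| 5.4.5 reduced models | No; they only delete terms | No |
| 5.4.5 predictions | No | No; one per regimen |
| 5.4.6 e-max model | No; one-for-one replacement | No |

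The ATV, PG, CG and treatment terms allow an additive shift in QTc with ATV-PG. They do not allow a different AQ or DEAQ slope. If stepwise removal drops ATV, PG and CG, the concentration terms predict the same effect in both arms at equal AQ and DEAQ exposure. Protocol 10.4.2 and 10.4.3 add no interaction or contrast.

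**2. Arm sizes.** The plan's counts reproduce: 20 + 24 = 44, and 8 + 3 × 12 = 44 (SAP 3.1).

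**3. Illustration of slope sharing.** Inputs from the documents are 12/12/12/8 subjects, 19 post-dose times, and the tmax and half-lives in Protocol section 1. Assumed inputs are:

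- one-compartment profiles scaled to peak 1;
- concentration log-SD 0.4 between and 0.15 within subjects;
- residual SD 7 ms and between-subject SD 5 ms;
- DEAQ slope CV 30%;
- AQ effect 3 ms;
- DEAQ effect 12.5 ms at peak for AQ alone, doubled in the combination.

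The true difference is (2 − 1) × 12.5 = 12.5 ms. Expected coefficients come from generalised least squares in the full 5.4.5 model. At equal exposure the difference between the two predictions is β_ATV + β_PG + β_CG, plus (treat_comb − treat_AQ) if treatment is included. The SAP does not say whether it is, so both are shown.

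- **Random intercept and DEAQ slope.** The shared DEAQ slope is 17.59 ms. On concentration terms the difference is 2.10 + 0.00 + 0.33 = 2.43 ms (19% of 12.5). With treatment it is 2.43 + 1.39 + 2.28 = 6.10 ms (49%). On concentration terms AQ alone is overstated by 5.11 ms and the combination understated by 4.96 ms.
- **Random intercept only.** The shared slope is 17.73 ms. The differences are 3.99 ms (32%) and 10.02 ms (80%). AQ alone is overstated by 5.23 ms and the combination understated by 3.27 ms on concentration terms.
- **Slope 1.5-fold (true difference 6.25 ms).** On concentration terms the errors are +2.53 and −2.48 ms (random slope), or +2.60 and −1.71 ms (intercept only). The predictions then differ by 6.25 − 2.53 − 2.48 = 1.24 ms, or 6.25 − 2.60 − 1.71 = 1.94 ms.

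A REML simulation (300 trials per setting, random intercept and DEAQ slope, 39 df in place of Kenward-Roger) gave:

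| True slope ratio | 1.0 | 1.5 | 2.0 |
|---|---|---|---|
| Shared DEAQ slope, ms | 12.5 | 15.2 | 17.7 |
| Difference, concentration terms, ms | 0.2 | 1.0 | 1.7 |
| Difference, with treatment, ms | 0.0 | 2.9 | 5.2 |
| Full model excluded by treatment F-test | 5% | 9% | 22% |

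With equal slopes there is no bias. With unequal slopes the treatment screen usually stays silent. A simpler simulation with other assumed values flagged a doubling or halving in about 29-30% of runs.

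**4. What added terms would deliver.** In the same REML simulation, a model with arm-specific AQ and DEAQ slopes estimated DEAQ differences of 0.1, 6.2 and 12.2 ms (true 0, 6.25, 12.5). The 90% half-width was about 5.0 ms and coverage 88-92%. It excluded zero in 11%, 64% and 99% of trials, and every fit converged. Over the ranges of assumed SDs tried, the half-width was 3.0-7.6 ms at a 12.5 ms effect and 4.8-13.4 ms at 30.9 ms.

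For the by-timepoint contrast, the residual df are 44 − 5 = 39 and the half-width is 1.685 × SD × √(1/8 + 1/12) = 0.769 × SD. That is 4.61, 6.15, 7.69 or 9.23 ms for an assumed ΔQTc SD of 6, 8, 10 or 12 ms.

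**The case against.** The objective can be read additively. On that reading the ATV, PG and CG coefficients with 90% intervals, and a prediction for each regimen, do address it. This stands in part: the objective is served indirectly, and the wording does not compel an interaction model.

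A reader might infer that the planned predictions are biased. The documents do not support that. Bias arises only if the slopes differ, and no fold change is given. Protocol section 1 expects low potential for a pharmacokinetic interaction, although it does not address a pharmacodynamic one. The 12.5 and 30.9 ms figures (Protocol 1.2.2.1) are for artesunate-amodiaquine in a study of malaria treatment, and the first is QTcB while the SAP models QTcF.

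A reader might also infer that the plan contains no sound comparison of the two arms. It does. The 5.4.4 differences use no concentration terms, so slope sharing does not touch them, and subtracting them gives combination minus AQ at each timepoint. SAP 5.4.6 also consults that analysis before accepting the primary model under the 10 ms rule. What is missing is the planned contrast and its interval.

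The illustrated errors belong to the full model and were not carried through stepwise removal, F-test exclusion and AIC selection. SAP 5.4.5 allows predictions from other models of interest, but names no interaction model. The study is exploratory and not formally sized (SAP 3.3), so any interval may be inconclusive. That argues for labelling the estimate, not for omitting it.

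**Conclusion.** The gap is real and follows from the model formulas alone. No model in SAP 5.4.5-5.4.6 can show a change in AQ or DEAQ slope, and neither 5.4.4 nor 5.4.5 plans a combination-minus-AQ contrast with an interval. The objective is met only through additive terms, arm-versus-placebo differences and separate predictions.

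The consequence is conditional. Equal slopes mean no bias. If the slope doubled from an assumed 12.5 ms, the two predictions would show about 2-4 ms of the true 12.5 ms on concentration terms, or about 5-10 ms with treatment included. Those sizes rest on the assumed profiles, SDs and fold change, and on the full model.

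The primary safety results are not affected. The point should be addressed, with medium confidence in its practical size.

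**What to change.** 1. **SAP 5.4.4:** add the combination-minus-AQ-alone contrast at each timepoint from the existing four-level treatment model, with a two-sided 90% confidence interval.
2. **SAP 5.4.5:** add one pre-specified exploratory model that always keeps the AQ and DEAQ concentrations and adds AQ × combination and DEAQ × combination terms to the fixed effects. Use a random intercept and a random DEAQ slope, or a random intercept only if that does not converge. Report both arms' slopes and their differences with two-sided 90% intervals, whatever the treatment F-test shows. State that this model does not alter the primary model selection or the e-max rule in 5.4.6.
3. **SAP 5.4.7:** draw the AQ and DEAQ regression lines separately for the AQ-alone and combination arms.

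The cost is SAP wording, one contrast and one extra model on data already collected. With 8 combination subjects the intervals will be wide: for the DEAQ slope difference, a half-width of about 3-8 ms at an assumed 12.5 ms effect and up to about 13 ms at 30.9 ms. Label the results exploratory, and state that an interval including zero is not evidence of no impact.
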